6.2.2.4. Time to response

Time to response (TTR) is defined, for participants with OR, as the time from the date of first dose of study treatment to the first documentation of objective response (CR or PR) which is subsequently confirmed.

$$\text{TTR (in months)} = [\text{first date of OR} - \text{date of first dose of study treatment} + 1] / 30.4375$$

TTR will be summarized using simple descriptive statistics (mean, SD, median, min, max, Q1, Q3).

6.2.2.5. Progression-free survival

Progression-Free Survival (PFS) is defined as the time from the date of first dose of study treatment to the date of the first documentation of PD or death due to any cause, whichever occurs first.

PFS data will be censored on the date of the last adequate tumor assessment for participants who do not have an event (PD or death), for participants who start a new anti-cancer therapy

prior to an event (see Section 5.2.6) or for participants with an event after 2 or more missing tumor assessments. Participants who do not have an adequate baseline tumor assessment or who do not have an adequate post-baseline tumor assessment will be censored on the date of first dose of study treatment unless death occurred on or before the time of the second planned tumor assessment (i.e. ≤ 16 weeks after the first dose of study treatment) in which case the death will be considered an event.

The censoring and event date options to be considered for the PFS analysis are presented in Table 11.

$$\text{PFS (months)} = [\text{date of event or censoring} - \text{date of first dose of study treatment} + 1] / 30.4375$$

Table 11. Outcome and Event Dates for PFS Analyses

Scenario	Date of event/censoring	Outcome
No adequate baseline assessment	Date of first dose of study treatment ^a	Censored ^a
PD or death - After at most one missing or inadequate post-baseline tumor assessment, OR - ≤ 16 weeks after the date of first dose of study treatment	Date of PD or death	Event
PD or death - After 2 or more missing or inadequate post-baseline tumor assessments	Date of last adequate tumor assessment ^b documenting no PD before new anti-cancer therapy is given or missed tumor assessments	Censored
No PD and no death	Date of last adequate tumor assessment ^b documenting no PD before new anti-cancer therapy is given or missed tumor assessments	Censored
Treatment discontinuation due to 'Disease progression' without documented progression	Not applicable	Information is ignored. Outcome is derived based on documented progression only.
New anti-cancer therapy given	Date of last adequate tumor assessment ^b documenting no PD before new anti-cancer therapy is given or missed tumor assessments	Censored

^a However if the participant dies ≤ 16 weeks after the first dose of study treatment and did not initiate new anti-cancer therapy, the death is an event with date on death date.

If there are no adequate post-baseline assessments prior to PD or death, then the time without adequate assessment should be measured from the first dose of study treatment; if the criteria were met the censoring will be on the date of the first dose of study treatment.

Kaplan-Meier estimates (product-limit estimates) will be presented by treatment group together with a summary of associated statistics including the median PFS time with 2-sided

95% CIs. In particular, the PFS rates at 6, 9, 12, 18, and 24 months will be estimated with corresponding 2-sided 95% CIs. The CIs for the median will be calculated according to Brookmeyer and Crowley (1982)² and the CIs for the survival function estimates at the time points defined above will be derived using the log-log transformation according to Kalbfleisch and Prentice (2002)⁶ (confotype=loglog default option in SAS Proc LIFETEST) with back transformation to a CI on the untransformed scale. The estimate of the standard error will be computed using Greenwood’s formula.

Frequency (number and percentage) of participants with each event type (PD or death) and censoring reasons will be presented by treatment group. Reasons for censoring will be summarized according to the categories in Table 12 following the hierarchy shown.

Table 12. PFS Censoring Reasons and Hierarchy

Hierarchy	Condition	Censoring Reason
1	No adequate baseline assessment	No adequate baseline assessment
2	Start of new anti-cancer therapy	Start of new anti-cancer therapy
3	Event after 2 or more missing or inadequate post-baseline tumor assessments/ first dose of study treatment	Event after missing assessments ^a
4	No event and [withdrawal of consent date \geq first dose of study treatment OR End of study (EOS) = Participant refused further follow-up]	Withdrawal of consent
5	No event and lost to follow-up in any disposition page	Lost to follow-up
6	No event and [EOS present OR disposition page for any epoch after screening says participant will not continue into any subsequent phase of the study] and no adequate post-baseline tumor assessment	No adequate post-baseline tumor assessment
7	No event and none of the conditions in the prior hierarchy are met	Ongoing without an event

^a 2 or more missing or inadequate post-baseline tumor assessments.

The PFS time or censoring time and the reasons for censoring will also be presented in a participant listing.

Time of Follow-Up for PFS

A plot will be generated to compare planned and actual relative day of tumor assessments by treatment group. A Kaplan-Meier plot for PFS follow-up duration will also be generated to assess the follow-up time in the treatment groups reversing the PFS censoring and event indicators.

6.2.2.6. Overall Survival

Overall survival (OS) is defined as the time from the first dose of study treatment to the date of death due to any cause. Participants last known to be alive will be censored at date of last contact.

$$\text{OS (months)} = [\text{date of death or censoring} - \text{date of first dose of study treatment}]$$

+1]/30.4375

Kaplan-Meier estimates (product-limit estimates) will be presented by sub-study and treatment group together with a summary of associated statistics including the median OS time with 2-sided 95% CIs. In particular, the OS rates at 6, 9, 12, 15, 18, and 24 months will be estimated with corresponding 2-sided 95% CIs. The CIs for the median will be calculated according to Brookmeyer and Crowley (1982)² and the CIs for the survival function estimates at the time points defined above will be derived using the log-log transformation according to Kalbfleisch and Prentice (2002)⁶⁶ (conftype=loglog default option in SAS Proc LIFETEST) with back transformation to a CI on the untransformed scale. The estimate of the standard error will be computed using Greenwood’s formula.

Frequency (number and percentage) of participants with an event (death) and censoring reasons will be presented by treatment group. Reasons for censoring will be summarized according to the categories in Table 13 following the hierarchy shown.

Table 13. OS Censoring Reasons and Hierarchy

Hierarchy	Condition	Censoring Reason
1	No event and [withdrawal of consent date \geq first dose of study treatment OR End of study (EOS) = Participant refused further follow-up]	Withdrawal of consent
2	No event and [lost to follow-up in any disposition page OR data cut-off date – last contact date > 16 weeks]	Lost to follow-up
3	No event and none of the conditions in the prior hierarchy are met	Alive

The OS time or censoring time and the reasons for censoring will also be presented in a participant listing.

Time of Follow-Up for OS

A Kaplan-Meier plot for OS follow-up duration will also be generated to assess the follow-up time in the treatment groups reversing the OS censoring and event indicators.

6.2.3. Pharmacokinetic endpoints

The following pharmacokinetic analyses will be based on the PK concentration analysis set by treatment group.

Concentrations for sasanlimab will be summarized descriptively (n, mean, SD, CV, median, minimum, maximum, geometric mean, its associated CV, and 95% confidence interval) by treatment group, cycle and day, and/or nominal time.

Individual participant and median profiles of the concentration-time data will be plotted by treatment group using nominal times, as appropriate. Median profiles may be presented as appropriate.

Trough concentrations (C_{trough}) for sasanlimab will be plotted using a box-whisker plot by treatment group, cycle and day.

Concentrations for encorafenib, binimetinib (Sub-Study A), axitinib, SEA-TGT (Sub-Study B) and any analyzed metabolites will be summarized descriptively (n, mean, SD, coefficient of variation (CV), median, minimum, maximum, geometric mean, its associated CV, and 95% confidence interval) by treatment group/dose, cycle, timepoint, and day (as applicable). Exclusions or separate summaries for dose modifications and concomitant medications may be considered in data summaries.

C_{trough} for encorafenib, binimetinib and applicable metabolites will be plotted for each treatment group, and/or dose level using a box whisker plot by cycle and day.

Trough concentrations (C_{trough}) will be directly observed from the respective concentration-time data. Dose-normalized PK parameters ($C_{\text{trough-DN}}$) may be reported, as appropriate.

6.2.4. Population pharmacokinetic endpoints

Pharmacokinetic and pharmacodynamic data from this study may be analyzed using modeling approaches and may also be pooled with data from other studies to investigate any association of drug exposure such as sasanlimab, encorafenib, and/or binimetinib including applicable metabolite(s) with biomarker levels or significant safety/efficacy endpoints. The results of these analyses, if performed, may be reported separately.

6.2.5. Biomarker endpoints

The following biomarker analyses will be based on the biomarker analysis set by treatment group.

Descriptive statistics for levels of PD-L1 expression, and number and percentage of participants with tumors categorized with baseline PD-L1 expression level high versus low will be presented by treatment group. Expression level will be provided prior to database release. Summaries of BOR will be presented by treatment group and by PD-L1 status.

For Sub-Study B, the above analyses will be conducted for local and central PD-L1 expression assessments including summary of concordant and discordant assessments.

6.2.6. Endpoints for immunogenicity data

The following immunogenicity analyses of sasanlimab for Sub-Study A and Sub-Study B, and for SEA-TGT for Sub-Study B only will be based on the immunogenicity analysis set by treatment group.

All analyses described below are performed by treatment group and for all treatment groups combined within a study, if deemed appropriate.

Blood samples for sasanlimab immunogenicity testing will be collected pre-dose on Cycle 1, 2, 3, 4 (Sub-Study B only), 5, 7, 10, and 13 and then every 6 cycles until EOT. All samples should be drawn within 6 hours before start of sasanlimab dosing. Additional samples for anti-sasanlimab and anti-SEA-TGT (Sub-Study B only) antibodies (and simultaneous PK

draws for measurement of respective study drugs) will be collected at the Day 30 Follow-up visit after the end of treatment.

Samples positive for ADA will be analyzed for titer and may be analyzed for nAb.

For the immunogenicity data, the percentage of participants with positive ADA and Nab each will be summarized by treatment. For participants with positive ADA or Nab, the magnitude (titer), time of onset, and duration of ADA or Nab response will also be described, if data permit.

Participants will be characterized into different ADA categories based on the criteria defined in Table 14.

Table 14. Participants Characterized Based on Anti-Drug Antibody Results (ADA Status) Category

Term	Definition
ADA-positive sample	ADA sample titer $\geq \text{Log}_{10}$ (99)
ADA-negative sample	ADA sample titer $< \text{Log}_{10}$ (99)
NAb-positive sample	NAb sample titer $\geq \text{Log}_{10}$ (4)
NAb-negative sample	NAb sample titer $< \text{Log}_{10}$ (4)
Pre-existing ADA/NAb	Positive ADA/NAb at baseline (e.g. day 1 pre-dose)
Cross-reactivity	This often refers to immunogenicity testing against an endogenous antigen, biosimilar reference product or another biotherapeutic within the same therapeutic class.
Subject-level immunogenicity analysis population	
ADA evaluable population	All subjects with ≥ 1 post-treatment ADA result.
NAb evaluable population	ADA-positive subjects with ≥ 1 post-treatment NAb result, plus all ADA-negative subjects. An ADA-positive subject without any post-treatment NAb data is excluded from the analysis population.
Subject-level definitions	
Treatment-induced ADA	Baseline ADA titer is missing or negative and subject has ≥ 1 post-treatment positive ADA titer.
Treatment-boosted ADA	Baseline ADA titer is positive and subject has a ≥ 4 -fold dilution increase in ADA titer from baseline in ≥ 1 post-treatment sample. Since the ADA titer is log10 transformed, a 4-fold dilution increase is equivalent to 0.602 unit increase in titer (log10) from baseline.
ADA-positive subject	A subject with ≥ 1 treatment-induced or treatment-boosted ADA response.
ADA-negative subject	An ADA evaluable subject without treatment-induced or treatment-boosted ADA response. Subject either has (1) all ADA-negative results throughout the study or (2) is ADA positive at baseline but did not become treatment-boosted post dose.
ADA incidence	The percent of ADA-positive subjects in a treatment group/cohort or study.
Treatment-induced NAb	Baseline NAb titer is missing or negative or ADA-negative and subject has ≥ 1 post-treatment positive NAb titer.
Treatment-boosted NAb	Baseline NAb titer is positive and subject has a ≥ 4 -fold dilution increase in NAb titer from baseline in ≥ 1 post-treatment sample. Since NAb titer is log10 transformed, a 4-fold dilution increase is equivalent to 0.602 unit increase in titer (log10) from baseline.
NAb-positive subject	An ADA-positive subject with ≥ 1 treatment-induced or treatment-boosted NAb response. For ADA-positive (treatment-boosted) subjects, subject is NAb positive only if the subject has ≥ 1 treatment-induced or treatment-boosted NAb response at the visit where the subject has a treatment-boosted ADA response. For visits where the subject did not show a boosted ADA response, the subject is classified as NAb-negative for the visit even if the subject has post-treatment positive NAb titer for that visit.
NAb-negative subject	(1) an ADA-negative subject or (2) an ADA-positive subject without treatment-induced or treatment-boosted NAb response (i.e. subject has all NAb-negative results throughout the study or subject is NAb positive at baseline but did not become treatment-boosted post dose).
NAb incidence	The percent of NAb-positive subjects in a treatment group/cohort or study.
Duration of ADA and NAb response (subject-level definitions):	
Transient ADA	An ADA-positive subject with (1) a treatment-induced or treatment-boosted ADA sample detected only at 1 sampling time (excluding the last time point) post-treatment, or (2) treatment-induced or treatment-boosted ADA samples detected at ≥ 2 time points where the first and last positive samples (irrespective of any negative samples in between) are separated by < 16 weeks, and the subject's last sample is ADA negative.

Term	Definition
Persistent ADA	An ADA-positive subject with first and last positive ADA samples (treatment-induced or treatment-boosted) detected over a period of ≥ 16 weeks post-treatment, irrespective of any negative samples in between.
Indeterminate ADA	An ADA-positive subject who is not persistent or transient.
Transient NAb	A NAb-positive subject with (1) a treatment-induced or treatment-boosted NAb sample detected only at 1 sampling time (excluding the last time point) post-treatment, or (2) treatment-induced or treatment-boosted NAb samples detected at ≥ 2 time points where the first and last positive samples (irrespective of any negative samples in between) are separated by < 16 weeks, and the subject's last sample is NAb negative or ADA negative.
Persistent NAb	A NAb-positive subject with first and last positive NAb samples (treatment-induced or treatment-boosted) detected over a period of ≥ 16 weeks post-treatment, irrespective of any negative samples in between.
Indeterminate NAb	A NAb-positive subject who is not persistent or transient.

Note: Duration of response (persistent, transient or indeterminate) definitions are only applicable to ADA (or NAb)-positive subjects.

The number and percentage of participants in each ADA and nAb category will be summarized.

All ADA and NAb data will be listed, and the number and percentage of participants in each ADA and NAb category will be summarized by treatment arm and overall. Incidence of ADA and NAb positive participants and time to first ADA and NAb detection will also be summarized by treatment group and overall. Data from samples collected at EOT will be presented in individual listings, but only data from EOT samples collected within 30 days of last dose of the respective agent and at predose (if the last dose was given at EOT visit) will be included in categorical assessments and summaries.

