Phase 2 Sub-Study A will enroll approximately 62 participants with BRAF^{V600}-mutated NSCLC and will evaluate the activity and safety of sasanlimab + encorafenib + binimetinib.

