3.2.4. Immunogenicity endpoints

- ADA and nAb (i.e., incidence) against sasanlimab (Sub-Study A), sasanlimab and SEA-TGT (Sub-Study B), as data permit

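### NAb incidence: Table 14 drops ADA-positive participants without a NAb result but keeps all ADA-negative ones, so incomplete testing will usually understate the rate

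*SAP*

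**What the plan says.** SAP section 6.2.6 sets the testing rule: "Samples positive for ADA will be analyzed for titer and may be analyzed for nAb". Titer is therefore planned for every ADA-positive sample and NAb is optional. No rule says which samples are chosen.

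Table 14 in the same section fixes the participant-level definitions:

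- The NAb evaluable population is "ADA-positive subjects with ≥ 1 post-treatment NAb result, plus all ADA-negative subjects". The next sentence adds: "An ADA-positive subject without any post-treatment NAb data is excluded from the analysis population".
- A NAb-positive participant is "An ADA-positive subject with ≥ 1 treatment-induced or treatment-boosted NAb response", so only ADA-positive participants can be NAb-positive.
- Every ADA-negative participant is classed as NAb-negative without a NAb assay.
- NAb incidence is "The percent of NAb-positive subjects in a treatment group/cohort or study". The row does not say whether the base is the NAb evaluable population or the whole group.

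Section 3.2.4 lists the endpoint as "ADA and nAb (i.e., incidence) against sasanlimab (Sub-Study A), sasanlimab and SEA-TGT (Sub-Study B), as data permit". For sasanlimab, NAb incidence is also a secondary endpoint in both phases of the Sub-Study A objectives table. Section 6.2.6 commits to summarizing it by treatment group and overall.

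**The concern.** The exclusion acts on one stratum only. An ADA-negative participant always adds one to the denominator and nothing to the numerator. An ADA-positive participant without a NAb result, who might be NAb-positive, leaves both. If testing is incomplete, the retained set therefore holds too large a share of certain negatives, and the reported incidence tends to fall as less testing is done. Treatment groups with different completeness of testing would not be comparable, and a low figure could reflect few assays as easily as few neutralizing antibodies. The planned summaries do not call for a count of untested ADA-positive participants beside the rate.

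**Working it through.** The SAP states no NAb rate, ADA rate or testing fraction, so there is no figure of its own to reproduce. Its one related figure, a 4-fold rise as 0.602 log10 units, is correct (log10 4 = 0.602).

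**Inputs.** The population rules come from Table 14. These quantities are assumptions:

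- a = proportion ADA-positive among ADA-evaluable participants
- t = fraction of ADA-positive participants with at least one post-treatment NAb result
- q_t, q_u = NAb-positive rate among tested and untested ADA-positive participants

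**Formulas.**

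- True incidence = a·t·q_t + a(1 − t)·q_u
- Incidence on the NAb evaluable population, R = a·t·q_t / (1 − a + a·t)
- The retained share is 1 − a(1 − t), so true incidence = R·[1 − a(1 − t)] + a(1 − t)·q_u, and true − R = a(1 − t)·(q_u − R)

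The last line settles the direction. R is too low when q_u exceeds R, too high when q_u is below R, and exact when t = 1.

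**Testing unrelated to NAb status** (q_t = q_u = q). The true value is a·q, and R divided by it is t / (1 − a(1 − t)), whatever q is:

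| a | t = 0.9 | t = 0.8 | t = 0.5 |
|---|---|---|---|
| 0.10 | 0.91 | 0.82 | 0.53 |
| 0.20 | 0.92 | 0.83 | 0.56 |
| 0.30 | 0.93 | 0.85 | 0.59 |

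For a = 0.20, for example, 0.9/(1 − 0.20 × 0.1) = 0.9/0.98 = 0.92 and 0.8/(1 − 0.20 × 0.2) = 0.8/0.96 = 0.83. In absolute terms, with a = 0.20 and q = 0.5 the true incidence is 10.0%, and R is 9.2% at t = 0.9, 8.3% at t = 0.8 and 5.6% at t = 0.5.

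**Other denominator.** If incidence is taken over the whole group, it is a·t·q_t. That counts every untested ADA-positive participant as negative and cannot exceed the truth. Under the same assumption its ratio to the truth is t, which is lower than the ratio above for every t strictly between 0 and 1.

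**Worked example at the Sub-Study A Phase 2 size** ("Phase 2 Sub-Study A will enroll approximately 62 participants"). Assume 12 ADA-positive, 6 of them tested, 3 of those NAb-positive, and 62 − 12 = 50 ADA-negative.

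- NAb evaluable population: 3/(50 + 6) = 3/56 = 5.4%
- Whole group as denominator: 3/62 = 4.8%
- If the untested behave like the tested: (12/62) × (3/6) = 6/62 = 9.7%
- Bounds: 3/62 = 4.8% if all 6 untested are negative, (3 + 6)/62 = 9/62 = 14.5% if all are positive

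The Table 14 figure of 5.4% lies near the bottom of the 4.8% to 14.5% range. It is too high only if none of the six untested is NAb-positive. With one positive the truth is already 4/62 = 6.5%.

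**The case against.** Several points against the concern are sound.

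First, a reader might infer that the rate is understated whenever any ADA-positive participant goes untested. That is not an identity. In the example, if all six untested are negative, 5.4% exceeds the true 4.8%. The reversal needs a NAb rate in the untested below that of the retained set, here 5.4% against 50% in the tested. The SAP states no selection rule that would make this likely, but it cannot be excluded.

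Second, a reader might infer that the denominator contains people of unknown NAb status. It does not. Under Table 14 every retained participant has a determinate status, and the excluded are the unknowns. This is a complete-case rule, in line with section 5.3.1, which analyzes data as observed. The criticism that stands is that missingness depends on ADA status.

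Third, the optional wording concerns samples, while exclusion requires that a participant has no post-treatment NAb result at all. Sampling repeats over many cycles and one result suffices, so optional sample testing need not leave many participants untested. Reporting is also subject to data availability: if the assay is run on all there is no bias, and if it is run on none nothing need be reported. Even so, the SAP writes a rule for untested participants, and that rule distorts the rate in the case it is written for.

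Fourth, the size can be modest. At a = 0.20, q = 0.5 and t = 0.9 the gap is 0.8 percentage points, against a standard error of about 3.8 points at n = 62 (√(0.10 × 0.90/62)). All ADA and NAb data will be listed, so the untested count can be recovered, but a listing does not correct the tabulated rate.

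**Conclusion.** The point holds conditionally. If only some ADA-positive participants have a NAb result and testing is unrelated to NAb status, NAb incidence on the Table 14 population is understated by the factor t/(1 − a(1 − t)). That is 8% too low at t = 0.9 and 17% too low at t = 0.8 for an assumed a of 0.20. Both a and t are assumptions, and the SAP does not indicate how complete testing will be. The unnamed denominator does not rescue the rate, because the whole-group reading lies lower still. A reader might go further and see a threat to the trial's main conclusions. The documents do not support that: the endpoint is secondary and descriptive, and no test, decision rule or sample size uses it. A correction is still worthwhile because the definition is wrong in the only situation where it operates, and the remedy needs no new testing.

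**What to change.** In section 6.2.6 and Table 14:

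1. Name the denominator in the NAb incidence row.
2. Report the NAb-positive proportion among ADA-positive participants who have a post-treatment NAb result, with the number of ADA-positive participants untested beside it, by treatment group and overall.
3. When any are untested, give bounds on NAb incidence with the untested taken as all negative and as all positive.
4. Optionally add ADA incidence multiplied by the tested proportion as a point estimate, stating that it assumes the tested represent the untested. The bounds do not need that assumption.

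If every ADA-positive participant has a NAb result, the present ratio is unbiased and can stand. The cost is a wording change, one or two extra table lines, and a wider reported range when testing is incomplete. Sample collection and assays are unchanged.
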